13.12.6. Efficacy Figures

Efficacy: Figures					
No.	Population	GSK Standard / Example Shell	Title	Programming Notes	Deliverable
Snapshot					
2.1.	Safety	SNAPSHOT8	Percent (95% CI) of Subjects with Plasma HIV-1 RNA ≥ 50 copies/mL Over Time (Intervention Phase) –Snapshot Analysis	Use Exact (Clopper-Pearson) method for 95% confidence Intervals. Drop '(Intervention Phase)', Observed cases to be used at EOS instead of Snapshot	M12, EOS
2.2.	Safety	SNAPSHOT8	Percent (95% CI) of Subjects with Plasma HIV-1 RNA < 50 copies/mL Over Time (Intervention Phase) –Snapshot Analysis	Use Exact (Clopper-Pearson) method for 95% confidence Intervals. Drop '(Intervention Phase)', Observed cases to be used at EOS instead of Snapshot	M12, EOS

Efficacy: Figures					
2.3.	Safety	SNAPSHOT10	Individual HIV-1 RNA Plasma Profiles by Visit for Subjects with HIV-1 RNA \geq 50 copies/mL at Month 12 per Snapshot Algorithm	The 1st vertical line indicates start of study treatment at Intervention Phase. The second vertical reference line indicates last IP on-treatment study day. i.e. min (last IP injection dose+35 days, LTFU HAART start date, date of last oral CAB+RPV+1). This vertical line is only for subjects who withdraw from Intervention Phase/Extension phase.	M12
2.4.	Safety	SNAPSHOT10	Individual HIV-1 RNA Plasma Profiles by Visit for Subjects with Confirmed Virologic Failure	Same as Figure 2.3.	M12, EOS

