HIV-1 infected participants who meet all eligibility criteria will be switched from their pre-baseline regimen to an oral regimen (CAB 30 mg + RPV 25 mg once daily) during the **oral lead-in phase**. Participants will return to the clinic, and if laboratory and clinical evaluations continue to support progression into the **injection treatment phase** of the study, will take the last dose of their oral regimen (CAB 30 mg + RPV 25 mg) and receive the first dose of CAB LA (600 mg) + RPV LA (900 mg) injections on the same day (Month 1). The participant will receive the second injections CAB LA (600 mg) + RPV LA (900 mg) one month later (Month 2). All subsequent injections will occur every two months thereafter (Month 4, Month 6, etc) for a total of 7 doses of CAB LA

and RPV LA (Table 7). The total length of the treatment phase is approximately one year.

Table 7 Dosing Regimen

Oral Lead-in to End of Study ⁺		
CAB + RPV Oral Lead-In		
Oral Lead-in (Day 1 to Month 1)	• Take one tablet of CAB 30 mg + RPV 25 mg once daily	
two once daily tablets taken with food		
CAB LA + RPV LA Injections		
Dose 1 (Month 1)	Receive last dose of oral CAB + RPV regimen	
	 Receive CAB LA 600 mg given as 1 X 3 mL IM injection 	
	 Receive RPV LA 900 mg given as 1 X 3 mL IM injection 	
Dose 2 to Dose 7 (Month 2- End of Study ⁺)	 Receive CAB LA 600 mg given as 1 X 3 mL IM injection 	
two 3 mL injections every two months	 Receive RPV LA 900 mg given as 1 X 3 mL IM injection 	
+Until after dose 7 (Month 12) when locally approved and commercially available, the participant no longer derives clinical benefit, the participant meets a protocol-defined reason for discontinuation or until development of CAB LA or RPV LA is terminated		

The dosing window for the second injections will be +0/-7 days from the projected target date (target date is established at Month 1). All subsequent injection windows (starting with Dose 3) will be +7/-7 days from the projected target date. Doses outside of the window *may* be allowed with prior Medical Monitor approval.

Participants will continue CAB LA + RPV LA until:

- After dose 7 and when the study intervention is locally approved and available for the Investigator to prescribe. Note if intervention is not locally approved at dose 7 they will continue into the Extension Phase (see Section 6.8).
- the participant no longer derives clinical benefit
- the participant meets a protocol-defined reason for discontinuation

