13.3.2. Treatment State

Within each study phase (based on assignment of study phase described in [Section 13.3.1](#)), only those events/assessments which occur within the ranges shown in Table 11 will be considered ‘on-treatment’ for the given phase. No treatment states will be assigned to medications.

For adverse events, partial AE start date will use imputation as described in 13.6.2.1.

Table 11 Treatment State within Study Phases

Study Phase	State	Definition
Screen	Pre-Treatment	All assessments/events within phase
Intervention/Extension	On-treatment	Date ≤ max (Date of Last CAB LA +RPV LA IM Dose + 63, Date of Last Dose of Oral Study Treatment (CAB+RPV or SOC Bridging) +1)
	Post-Treatment	Date > max (Date of Last CAB LA +RPV LA IM Dose + 63, Date of Last Dose of Oral Study Treatment (CAB+RPV or SOC Bridging) +1)
Long Term Follow-Up	Post-Treatment	All assessments/events within phase
NOTES: 
 • Date = Assessment/Start Date a. Treatment State is determined after data has been assigned to the study phases as defined in Section 13.3.1. b. Last injection and/or last dose of oral study treatment (CAB+RPV or SOC bridging) are only applied to participants who permanently discontinued the study treatment. The assessments for participants who did not permanently discontinue the study treatment will be considered ‘On-treatment’. For participants continuing into extension phase, all data assigned to intervention phase per Section 13.3.1 will be considered ‘On-treatment’. 		

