1. If non-permitted change in background therapy prior to Month 12	HIV-1 RNA \geq 50	Change in background therapy
2. If non-permitted change in background therapy during Month 12		

 Last on-treatment VL during Month 12 prior to/on the date of change \geq 50 c/mL 	HIV-1 RNA \geq 50	Data in window not below 50

 Last on-treatment VL during Month 12 prior to/on the date of change $<$ 50 c/mL 	HIV-1 RNA $<$ 50	

 No VL during Month 12 prior to/on the date of change 	HIV-1 RNA \geq 50	Change in background therapy
3. If none of the above conditions met		
3.1. On-treatment VL available during Month 12		

 Last on-treatment VL during Month 12 \geq 50 c/mL 	HIV-1 RNA \geq 50	Data in window not below 50

 Last on-treatment VL during Month 12 $<$ 50 c/mL 	HIV-1 RNA $<$ 50	
3.2. No on-treatment VL during Month 12		
3.2.1. If participants are still on study, i.e. a participant has not permanently discontinued the study treatment yet, or if a participant permanently discontinued the study treatment and the upper bound of analysis snapshot window is prior to the following date: 
 Min[max(Date of last injection + 35, Date of Last Dose of Oral Study Treatment (CAB+RPV, SOC Bridging) + 1), LTFU ART Start Date] 		
3.2.1.1. If no on-treatment VL during Month 12 is not due to COVID-19	No virologic data at Month 12 Window	On study but missing data in window (Non-COVID-19 related)
3.2.1.2. If no on-treatment VL during Month 12 is due to COVID-19	No virologic data at Month 12 Window	On study but missing data in window (COVID-19 related)

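### For withdrawn, injected participants without oral CAB+RPV bridging, the last-on-treatment line in SAP Figures 2.3 and 2.4 always falls on the day after Dose 1

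*SAP*

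**What the plan says.** The programming note to Figure 2.3 in SAP 13.12.6 states the purpose of the line: "The second vertical reference line indicates last IP on-treatment study day". It then gives the date as "min (last IP injection dose+35 days, LTFU HAART start date, date of last oral CAB+RPV+1", a single minimum over three terms, and limits who gets it: "This vertical line is only for subjects who withdraw from Intervention Phase/Extension phase". Figure 2.4, the profiles of confirmed virologic failures, takes the rule over unchanged ("Same as Figure 2.3"). Figure 2.3 is produced at Month 12, and Figure 2.4 at Month 12 and at end of study.

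Elsewhere the SAP treats the oral date differently. Table 11 in 13.3.2 takes the maximum of the last injection date plus 63 days and "Date of Last Dose of Oral Study Treatment (CAB+RPV or SOC Bridging) +1". Tables 1 to 3 in 13.2.1 start follow-up after the smaller of the long-term follow-up (LTFU) ART start date and that same maximum. Snapshot step 3.2.1 in 13.8 is nested in the same way, although with 35 days: "Min[max(Date of last injection + 35, Date of Last Dose of Oral Study Treatment".

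Protocol 4.3.3 ties the end of the lead-in to Dose 1. The participant "will take the last dose of their oral regimen (CAB 30 mg + RPV 25 mg) and receive the first dose of CAB LA" on the same day, at Month 1.

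**The concern.** A minimum over the last oral date makes sense only if oral dosing comes at the end of treatment. In this trial it comes at the beginning. Every participant takes oral CAB+RPV in the lead-in, so the oral term is present for everyone. Unless oral CAB+RPV is taken again as bridging, it is fixed at the day after Dose 1. Later injections move only the first term, which can never be the smallest.

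These are the only plots of individual virologic courses in the SAP's list of efficacy figures, and Figure 2.4 shows the cases that a reader will study most closely. Protocol 7.1.8.3 requires study treatment to be discontinued after confirmed failure, so those participants are the ones for whom the line is drawn. A failure on long-acting drug would look like a rebound after stopping.

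**Working it through.** The plan gives no numerical example, so there is no figure to reproduce. The check puts dates into the printed rule and into the SAP's nested rule.

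**Inputs**
- Printed rule (SAP 13.12.6): P = min(last injection + 35, LTFU ART start, last oral CAB+RPV + 1).
- Nested rule (SAP 13.2.1, Tables 1 to 3): N = min(LTFU ART start, max(last injection + 63, last oral + 1)).
- Last lead-in tablet on the day of Dose 1 (Protocol 4.3.3).
- Scheduled HIV-1 RNA after Dose 1 at Months 2, 4, 8 and 12 (Protocol 1.3, Table 1).
- Assumptions for illustration: 30-day months; Dose 1 and last lead-in tablet on Day 30; where an LTFU ART date is used, it is 60 days after the last injection.

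**No bridging, withdrawn.** The oral term is 30 + 1 = 31. For a last injection at Month 8 (Day 240):
- P = min(240 + 35, 300, 31) = min(275, 300, 31) = Day 31.
- N with no LTFU ART date = max(240 + 63, 31) = Day 303.
- N with LTFU ART on Day 300 = min(300, 303) = Day 300.

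The same arithmetic for each possible last injection:

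| Last injection | Day | Printed | Nested, no LTFU ART date | Nested, LTFU ART at +60 |
|---|---|---|---|---|
| Month 1 | 30 | 31 | 93 | 90 |
| Month 2 | 60 | 31 | 123 | 120 |
| Month 4 | 120 | 31 | 183 | 180 |
| Month 6 | 180 | 31 | 243 | 240 |
| Month 8 | 240 | 31 | 303 | 300 |
| Month 10 | 300 | 31 | 363 | 360 |
| Month 12 | 360 | 31 | 423 | 420 |

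The scheduled viral loads after Dose 1 fall on about Days 60, 120, 240 and 360. All lie to the right of Day 31.

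**Range for the correct line.** If LTFU ART does not start before the last injection, N lies between the last injection day and that day plus 63. For a last injection at Month 8 this is Day 240 to Day 303, so the printed line is 240 − 31 = 209 to 303 − 31 = 272 days too early.

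**35 against 63 days.** With 63 in the printed rule, P = min(303, 300, 31) = Day 31. The line does not move, so this is a separate matter from the number of days.

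**Bridged, then back on injections.** Bridging ends on Day 239, last injection Day 240, LTFU ART Day 300. P = min(275, 300, 240) = Day 240; N = min(300, max(303, 240)) = Day 300. The line is 60 days early, but a rebound on Day 120 is correctly drawn as on treatment.

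**Withdrawn in the lead-in, never injected.** There is no injection date, and the oral term correctly sets the line.

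**The case against.** The strongest case on the other side has four parts.

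First, the oral term may have been meant for bridging only. The text does not say so. Where the SAP means the end of bridging, as in the LTFU study day in 13.5.1, it names bridging. Even on that reading, the single minimum goes wrong for someone who bridged and resumed injections, as the last worked dates for a bridged participant show.

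Second, the line is a display aid. This stands. Snapshot categories follow 13.8, confirmed failure follows 13.5.3 and treatment state follows Table 11. Table 2.10, Listing 12 and Listing 36 report viral loads, genotypes and visit dates for the same people without the line, which limits the risk of misreading.

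Third, a reader might count the absence of standard-of-care (SOC) bridging as a further error. The documents do not support that. The line is labelled as the end of IP, Protocol 6.1 limits IP to oral and long-acting cabotegravir and rilpivirine, and SAP 13.5.4 subtracts SOC bridging to obtain IP exposure. Leaving it out fits the label. What remains open is which of the two endpoints the line is meant to mark.

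Fourth, last injection plus 63 days is an upper limit for the correct line. Protocol 4.3.4 has HAART begin once virologic failure is confirmed, so among confirmed failures the LTFU ART date will often set it. This shortens the error without removing it, because the correct line still cannot precede the last injection unless ART does.

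**Conclusion.** The note is wrong as written and conflicts with Tables 1 to 3, with the maximum in Table 11 and with Snapshot step 3.2.1. Nothing elsewhere in the SAP overrides it. For withdrawn, injected participants who never took oral CAB+RPV bridging, the line is fixed at the day after Dose 1, and all viral loads after that day are drawn as off treatment. For those who bridged and resumed injections, the line can also fall too early. The size depends on the last injection: with Month 8 it is about 209 to 272 days, under the 30-day-month assumption and LTFU ART not before the last injection.

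A reader might infer that every rebound on injections is drawn as off treatment. That goes too far. The line appears only for participants who withdraw. Figure 2.3 can include people at or above 50 c/mL who stay on treatment, since Protocol 7.1.8.1 requires no change of therapy below 200 c/mL, and they have no line. In bridged participants, a rebound before the end of bridging is shown correctly. The effect is close to complete only in Figure 2.4, among withdrawn failures without bridging. Nor is Table 11 by itself the full rule for the line: it contains no LTFU ART term, which comes from Tables 1 to 3. No estimate, interval or failure count changes.

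**What to change.** In SAP 13.12.6, replace the note for Figures 2.3 and 2.4 with the rule of Tables 1 to 3: line at min(LTFU ART start date, max(last CAB LA + RPV LA injection + the on-treatment days in Table 11, last oral dose + 1)), still only for participants who withdraw. State whether the line marks the end of IP, in which case the oral term covers oral CAB+RPV only, or the end of study treatment, in which case it includes SOC bridging, and label it to match. In the same edit, reconcile the 35 days in this note and in Snapshot step 3.2.1 with the 63 days in Table 11. The cost is one line of programming specification for both figures. No data collection, table or analysis rule changes because of the new line.

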13.12.7. Safety Tables

Safety: Tables					
No.	Population	GSK Standard/ Example Shell	Title	Programming Notes	Deliverable
Exposure					
3.1.	Safety	207966/primary_15/T3.1	Summary of Exposure to Study Treatment by Implementation Arm (Intervention Phase)	Includes Oral Bridging	IA2, M12
3.2.	Safety	207966/primary_15/T3.1	Summary of Exposure to Study Treatment by Implementation Arm	Includes Oral Bridging	M12, EOS
3.3.	Safety	SAF T1	Summary of Adherence to CAB LA + RPV LA Dosing Schedule by Visit, Country, and Site (Intervention Phase)	See Section 13.5.2 for Covid Impact Remove Covid-19 impact results from IA1.	IA1, IA2, HL, M12
3.4.	Safety	SAF T2	Summary of Adherence to CAB LA + RPV LA Dosing Schedule by Visit and Subgroup (Intervention Phase)	See Section 13.5.2 for Covid Impact Include all subgroups listed in Section 5.4.2 except for Site & Country	HL, M12
3.5.	Safety	SAF T1	Summary of Adherence to CAB LA + RPV LA Dosing Schedule by Visit, Country, and Site	See Section 13.5.2 for Covid Impact	EOS
3.6.	Safety	SAF T2	Summary of Adherence to CAB LA + RPV LA Dosing Schedule by Visit and Subgroup	See Section 13.5.2 for Covid Impact Include all subgroups listed in Section 5.4.2 except for Site & Country	EOS

CONFIDENTIAL

213199

Safety: Tables					
3.7.	Safety	Study 201584 (primary_02): Table 3.114	Summary of Categorized Needle Length and Gauge for CAB Injection		M12, EOS
3.8.	Safety	Study 201584 (primary_02): Table 3.115	Summary of Categorized Needle Length and Gauge for RPV Injection		M12, EOS
Adverse Events (AEs)					
3.9.	Safety	AE99	Adverse Event Overview by Study Phase and Overall	High level summary to include counts of overall AEs, Serious AEs, AEs leading to withdrawal, related AEs, AEs related to Covid-19, AEs related to Covid-19 leading to withdrawal, fatal AEs Overall breakdown to be condensed to Int + Ext phases.	HL, M12, EOS
3.10.	Safety	AE3	Summary of Adverse Events by Overall Frequency	ICH E3	M12, EOS
3.11.	Safety	AE5B	Summary of Adverse Events by System Organ Class and Maximum Grade	ICH E3	HL, M12, EOS
3.12.	Safety	AE5B	Summary of Adverse Events by System Organ Class and Maximum Grade — Excluding Study Drug Injection Site Reactions		M12, EOS
3.13.	Safety	AE5B	Summary of Adverse Events by System Organ Class and Maximum Grade (Oral Lead-in Period)		M12
3.14.	LTFU	AE5B	Summary of Adverse Events by System Organ Class and Maximum Grade (Long Term Follow-up Period)		M12, EOS
3.15.	Safety	AE3	Summary of Common ($\geq 5\%$) Adverse Events by Overall Frequency	ICH E3	M12, EOS
3.16.	Safety	AE3	Summary of Common ($\geq 1\%$) Grade 2-5 Adverse Events by Overall Frequency	ICH E3	M12, EOS

CONFIDENTIAL

213199

Safety: Tables					
3.17.	Safety	201584/primary_7/T3.46	Summary of Adverse Events by Visit and Maximum Severity – Overall and Common		HL, M12, EOS
3.18.	Safety	AE3	Summary Drug-Related Adverse Events by Overall Frequency	ICH E3	M12, EOS
3.19.	Safety	AE5B	Summary of Drug-Related Adverse Events by System Organ Class and Maximum Grade	ICH E3	HL, M12, EOS
3.20.	Safety	AE5B	Summary of Drug-Related Adverse Events by System Organ Class and Maximum Grade (Oral Lead-in Period)	ICH E3	M12
3.21.	LTFU	AE5B	Summary of Drug-Related Adverse Events by System Organ Class and Maximum Grade (Long Term Follow-up Period)	ICH E3	M12, EOS
3.22.	Safety	AE5B	Summary of Drug-Related Adverse Events by System Organ Class and Maximum Grade — Excluding Study Drug Injection Site Reactions		M12, EOS
3.23.	Safety	AE15	Summary of Common ($\geq 5\%$) Non-serious Adverse Events by System Organ Class and Preferred Term (Number of Subjects and Occurrences)	FDAAA, EudraCT	M12, EOS
3.24.	Safety	AE3	Summary of Common ($\geq 1\%$) Drug-Related Grade 2-5 Adverse Events by Overall Frequency	ICH E3	M12, EOS
3.25.	Safety	AE3	Summary of Non-Serious Drug-Related Adverse Events by Overall Frequency	Plain Language Summary requirements.	M12, EOS
3.26.	Safety	201584/primary_7/T3.46	Summary of Drug-Related Adverse Events by Visit and Maximum Severity – Overall and Common		M12, EOS
Serious and Other Significant Adverse Events					
3.27.	Safety	AE5B	Summary of Serious Adverse Events by System Organ Class and Maximum Grade	ICH E3	HL, M12, EOS

CONFIDENTIAL

213199

Safety: Tables					
3.28.	Safety	AE5B	Summary of Serious Adverse Events by System Organ Class and Maximum Grade (Oral Lead-in Period)	ICH E3	M12
3.29.	LTFU	AE5B	Summary of Serious Adverse Events by System Organ Class and Maximum Grade (Long Term Follow-up Period)	ICH E3	M12, EOS
3.30.	Safety	AE16	Summary of Serious Adverse Events by System Organ Class and Preferred Term (Number of Subjects and Occurrences)	FDAAA, EudraCT	M12, EOS
3.31.	Safety	201584/primary_7/T3.46	Summary of Serious Adverse Events by Visit and Maximum Severity – Overall and Common		M12, EOS
3.32.	Safety	AE1	Summary of Adverse Events Leading to Permanent Discontinuation of Study Treatment or Withdrawal from Study by System Organ Class and Preferred Term	GSK Statistical Display Standard	HL, M12, EOS
3.33.	Safety	AE1	Summary of Adverse Events Leading to Permanent Discontinuation of Study Treatment or Withdrawal from Study by System Organ Class and Preferred Term (Oral Lead-in Period)	GSK Statistical Display Standard	M12
3.34.	LTFU	AE1	Summary of Adverse Events Leading to Permanent Discontinuation of Study Treatment or Withdrawal from Study by System Organ Class and Preferred Term (Long Term Follow-up Period)	GSK Statistical Display Standard	M12, EOS
3.35.	Safety	201584/primary_7/T3.46	Summary of Adverse Events Leading to Permanent Discontinuation of Study Treatment or Withdrawal from Study by Visit and Maximum Severity – Overall and Common		M12, EOS

Safety: Tables					
3.36.	Safety	AE1	Summary of Serious Adverse Events Leading to Permanent Discontinuation of Study Treatment or Withdrawal from Study by System Organ Class and Preferred Term	GSK Statistical Display Standard	M12, EOS

CCI

Laboratory: Chemistry					
3.40.	Safety	LB1	Summary of Chemistry Changes from Baseline	ICH E3	M12, EOS
3.41.	LTFU	LB1	Summary of Chemistry Changes from Baseline (Long Term Follow-up Population)	ICH E3	M12, EOS
3.42.	Safety	LB16	Summary of Chemistry Results by Maximum Grade Increase Post-Baseline Relative to Baseline	ICH E3	HL, M12, EOS
Laboratory: Hematology					
3.43.	Safety	LB1	Summary of Hematology Changes from Baseline	Includes pre-specified parameters repeated in conventional units.	M12, EOS
3.44.	LTFU	LB1	Summary of Hematology Changes from Baseline (Long Term Follow-up Population)	Includes pre-specified parameters repeated in conventional units.	M12, EOS
3.45.	Safety	LB16	Summary of Hematology Results by Maximum Grade Increase Post-Baseline Relative to Baseline	ICH E3	HL, M12, EOS
Laboratory: Hepatobiliary (Liver)					

Safety: Tables					
3.46.	Safety	LIVER1	Summary of Liver Monitoring/Stopping Event Reporting	GSK Statistical Display Standard	M12, EOS
3.47.	Safety	LIVER10	Summary of Post Baseline Hepatobiliary Laboratory Abnormalities	GSK Statistical Display Standard See hepatobiliary abnormality criteria Section 13.7.1	HL, M12, EOS
3.48.	Safety	LIVER11	Summary of Liver Restart/Re-Challenges	GSK Statistical Display Standard	M12, EOS
Vital Signs					
3.49.	Safety	VS1	Summary of Change from Baseline in Vital Signs	ICH E3 Include Baseline values, weight, and BMI	M12, EOS
Cardiovascular Risk Factors					
3.50.	Safety	FH1	Summary of Family History of Cardiovascular Risk Factors	GSK Statistical Display Standard	M12
3.51.	Safety	SU1	Summary of Substance Use	GSK Statistical Display Standard	M12
COVID-19 Adverse Events					
3.52.	Safety	PAN1	Summary of COVID-19 Assessments for Subjects with COVID-19 Adverse Events	GSK Statistical Display Standard Includes events across all phases	IA2, M12, EOS
3.53.	Safety	PAN2	Summary of COVID-19 Additional Assessments for Subjects with COVID-19 Adverse Events	GSK Statistical Display Standard Includes events across all phases	M12, EOS
3.54.	Safety	PAN3	Summary of COVID-19 Symptoms for Subjects with COVID-19 Adverse Events	GSK Statistical Display Standard Includes events across all phases	M12, EOS
3.55.	Safety	PAN10	Incidence of Covid-19 Adverse Events Overall and by Subgroup	Subgroups include Sex, Implementation Arm Includes events across all phases	M12, EOS

[figure not shown]
Safety: Tables					
Adverse Events of Special Interest					
3.56.	Safety	201584/primary_27/T3.140	Summary of Depression, Anxiety and Suicidal or Suicidal Ideation/Behaviour Adverse Events by System Organ Class, Maximum DAIDS Toxicity Grade, and History of Depression, Anxiety or Suicidal Ideation/Behaviour at Screening		M12, EOS
3.57.	Safety	201584/primary_07/T3.122	Summary of Depression Adverse Events of Special Interest by System Organ Class and Preferred Term (Number of Subjects and Occurrences)		M12, EOS
3.58.	Safety	201584/primary_07/T3.125	Summary of Anxiety Adverse Events of Special Interest by System Organ Class and Preferred Term (Number of Subjects and Occurrences)		M12, EOS
3.59.	Safety	201584/primary_07/T3.128	Summary of Suicidal Ideation/Behaviour Adverse Events of Special Interest by System Organ Class and Preferred Term (Number of Subjects and Occurrences)		M12, EOS
3.60.	Safety	201584/primary_07/T3.134	Summary of Seizures Adverse Events of Special Interest by System Organ Class and Preferred Term (Number of Subjects and Occurrences)		M12, EOS
3.61.	Safety	201584/primary_07/T3.137	Summary of Hepatic Safety Profile: Assessment of Risk of Hepatotoxicity Adverse Events of Special Interest by System Organ Class and Preferred Term (Number of Subjects and Occurrences)		M12, EOS
3.62.	Safety	201584/primary_07/T3.140	Summary of Hypersensitivity Reactions (HSR) Adverse Events of Special Interest by System Organ Class and Preferred Term (Number of Subjects and Occurrences)		M12, EOS
3.63.	Safety	201584/primary_07/T3.143	Summary of Rash Adverse Events of Special Interest by System Organ Class and Preferred Term (Number of Subjects and Occurrences)		M12, EOS

CONFIDENTIAL

213199

Safety: Tables					
3.64.	Safety	201584/primary_07/T3.149	Summary of Bipolar Disorder Adverse Events of Special Interest by System Organ Class and Preferred Term (Number of Subjects and Occurrences)		M12, EOS
3.65.	Safety	201584/primary_07/T3.152	Summary of Psychosis Adverse Events of Special Interest by System Organ Class and Preferred Term (Number of Subjects and Occurrences)		M12, EOS
3.66.	Safety	201584/primary_07/T3.155	Summary of Mood Disorders Adverse Events of Special Interest by System Organ Class and Preferred Term (Number of Subjects and Occurrences)		M12, EOS
3.67.	Safety	201584/primary_07/T3.158	Summary of Sleep Disorders Adverse Events of Special Interest by System Organ Class and Preferred Term (Number of Subjects and Occurrences)		M12, EOS
3.68.	Safety	201584/primary_07/T3.161	Summary of Hyperglycaemia Adverse Events of Special Interest by System Organ Class and Preferred Term (Number of Subjects and Occurrences)		M12, EOS
3.69.	Safety	201584/primary_07/T3.161	Summary of Weight Gain Adverse Events of Special Interest by System Organ Class and Preferred Term (Number of Subjects and Occurrences)		M12, EOS
3.70.	Safety	201584/primary_07/T3.164	Summary of Rhabdomyolysis Adverse Events of Special Interest by System Organ Class and Preferred Term (Number of Subjects and Occurrences)		M12, EOS
3.71.	Safety	201584/primary_07/T3.167	Summary of Pancreatitis Adverse Events of Special Interest by System Organ Class and Preferred Term (Number of Subjects and Occurrences)		M12, EOS
3.72.	Safety	201584/primary_07/T3.170	Summary of Impact on Creatinine Adverse Events of Special Interest by System Organ Class and Preferred Term (Number of Subjects and Occurrences)		M12, EOS

Safety: Tables					
3.73.	Safety	201584/primary_07/T3.173	Summary of Safety in Pregnancy Adverse Events of Special Interest by System Organ Class and Preferred Term (Number of Subjects and Occurrences)		M12, EOS
3.74.	Safety	207966/primary_15/T3.109	Summary of Characteristics of Adverse Events of Special Interest		M12, EOS
3.75.	Safety	AE99	Adverse Event Overview by Study Phase and Subgroup	Repeat Table 3.9 for all relevant subgroups including country, sex, age group, race group, and CD4 group as mentioned in Section 5.4.2 . Do not include LTFU data. Include BMI >=30/<30 as a subgroup	M12

Safety: Tables

3.88.	Safety	VS1	Summary of Change from Day 1 Weight Values	Repeat of Table 3.49 using Day 1 values as Baseline.	EOS
-------	--------	-----	--	--	-----

